Title	A Phase III, Randomized, Open Label, Clinical Trial Evaluating the Augmentation of Anti-SARS-CoV-2 Immunity in Kidney Transplant Recipients via a Heterologous Additional Dose with Janssen Ad26.CoV2.S Vaccine
Running Title	Additional Dose with Janssen Ad26.CoV2.S Vaccine in Kidney Transplant Recipients
Protocol Number	21-008036
Phase	III
Methodology	Prospective, randomized, open label clinical trial
Overall Study Duration	Three years.
Subject Participation Duration	Each subject will be followed for two years. Vaccinated subjects will be followed for two years after their last dose of the Janssen Ad26.CoV2.S vaccine.
Single or Multi-Site	Multiple (3 Mayo Clinic Transplant sites)
Objectives	
Primary Objectives
 
 1. To assess whether an anti-SARS-CoV-2 spike protein antibody level of ≥ 250 U/mL can be achieved 28 days after a dose of the Janssen Ad26.CoV2.S vaccine in kidney transplant recipients who did not form acceptable levels of anti-SARS-CoV-2 spike protein antibody (< 250 U/ml but > 0 U/mL) after receiving two or more doses of a mRNA vaccine: Pfizer-BioNTech (BNT162b2 vaccine) or Moderna (mRNA-1273). This includes any combination of the Pfizer-BioNTech (BNT162b2 vaccine) or the Moderna (mRNA-1273) results in two or more doses of mRNA vaccine. 2. To compare whether a dose of the Janssen Ad26.CoV2.S vaccine can achieve an anti-SARS-CoV-2 spike protein level ≥ 250 U/mL in kidney transplant recipients with no detectable anti-SARS-CoV-2 spike protein antibody after two or more mRNA vaccines. Kidney transplant recipients will be randomized to either maintenance of current immunosuppression or adjustment in immunosuppression around the time of receiving the Janssen Ad26.CoV2.S vaccine. The number of subjects with anti-SARS-CoV-2 spike protein level ≥ 250 U/mL between the two randomized groups will be compared.

	
Secondary Objectives
 
 1. To determine the response* of the Janssen Ad26.CoV2.S vaccine in the subset of subjects who did not respond to an additional dose of the Janssen Ad26.CoV2.S vaccine in Segment I while on their maintenance immunosuppression. In this instance immunosuppression is adjusted (Segment II). 2. To determine the incidence of COVID-19 infection up to 2 years after enrollment or additional dose in all enrolled kidney transplant recipients (received Janssen Ad26.CoV2.S vaccine or not). 3. To determine the safety of an additional dose with the Janssen Ad26.CoV2.S vaccine after two or more doses of mRNA vaccine including vaccination with or without immunosuppression adjustment. 
*Response is defined as achieving an anti-SARS-CoV-2 spike protein antibody level ≥ 250 U/ml 28 days after an additional dose with the Janssen Ad26.CoV2.S vaccine.

	
Exploratory Objective
 
 1. To perform exploratory in vitro assays to better understand the mechanisms of response to COVID-19 vaccination.
Number of Subjects	Up to 1200 kidney transplant recipients at least 90 days after transplantation. 400 patients with low or no anti-SARS-CoV-2 spike protein antibody levels will receive one or two additional doses of the Janssen Ad26.CoV2.S vaccine per protocol. Approximately 800 kidney transplant recipients who had a good response to mRNA vaccines will be followed for 2 years for COVID infection and other outcomes.
Diagnosis and Main Inclusion	Kidney transplant recipient who have previously received two or more COVID-19 vaccinations (either the Pfizer or Moderna vaccines).
Study Product, Dose, Route, Regimen	
Janssen Ad26.CoV2.S, vaccine. The Janssen Ad26.COV2.s vaccine will be supplied at a concentration of 1×10^{11} vp/mL in single-use vials, with an extractable volume of 0.5 mL, and dose at 5×10^{10} vp. All participants will receive a single 0.5 mL dosage, typically in the deltoid.
 
Segment I—one dose Segment II—two doses (see protocol)

Duration of Administration	Each dose will be a single dose of Janssen Ad26.CoV2.S vaccine
Reference therapy	No

Statistical Methodology	A chi-square test will be used to assess whether there is a statistically significant difference in the response rate for subjects receiving an additional dose with the Janssen Ad26.CoV2.S vaccine either with immunosuppression reduction (N = 150) or without reduction (N = 150).
-------------------------	--

1. Introduction

This document is a protocol for a human research study. This study will be carried out in accordance with the applicable United States government regulations and Mayo Clinic research policies and procedures.

1.1 Background

As of October 1, 2021, the novel severe acute respiratory syndrome coronavirus 2 (SARS-CoV-2) has infected more than 219 million people globally[1], resulting in more than 4.55 million deaths. Unprecedented scientific effort has led to advances in understanding the biology of the virus, pathogenesis of disease, modes of transmission, and treatment approaches. Despite this, the morbidity and mortality from infection remains unacceptably high, and a greater emphasis on disease prevention afforded by a variety of vaccines is proving effective in reducing incidence of disease.

[figure not shown]
Within the United States, the FDA has granted full approval for the Pfizer and Moderna vaccines and emergency use authorization (EUA) for the Janssen vaccine, Janssen Ad26.CoV2.S. In phase III trials, the two-dose Moderna mRNA vaccine showed 94.1% efficacy at preventing COVID-19 illness, including severe disease[2]. The Pfizer mRNA two-dose vaccine conferred 95% protection against COVID-19 in persons 16 years of age or older[3]. The Janssen Ad26.CoV2.S vaccine uses a single dose, adenoviral delivery platform that has been used in other vaccine campaigns. Recently-published data from the initial trial (the ENSEMBLE trial) demonstrated that Janssen Ad26.CoV2.S vaccination was 85 percent effective against severe/critical disease[4]. Additionally, the trial met its co-primary endpoints of protecting against moderate to severe COVID-19 at 14 and 28 days after vaccination, achieving 67 percent efficacy at 14 days after vaccination; and 66 percent efficacy at 28 days after vaccination, with prevention against COVID-19-related hospitalization and death across all participants (N=44,325). Protection was generally consistent across race, age groups, including adults over 60 years of age (N=14,672), and those with and without comorbidities. There was also robust immunogenicity across both humoral on cell mediated effector arms[4].

Optimal vaccine induced immunity requires functional immune effector arms. In the general population, almost all recipients of the mRNA vaccine developed anti-SARS-CoV-2 spike protein levels of ≥ 250 U/ml[5]. In contrast, immunocompromised populations have reduced quantitative responses to COVID vaccines compared to non-immunocompromised populations. For example, in 658 transplant recipients who received 2 doses of SARS-CoV-2 mRNA vaccine, 301 (46%) had no antibody response after dose 1 or dose 2 [6]. Quantitative levels of anti-SARS-CoV-2 spike protein

antibodies also appeared lower than in non-immunocompromised hosts. These data are aligned with available data across a broad range of vaccines in solid organ transplant recipients suggesting lower humoral response rates (approximately 50%–70%) compared to non-transplant populations [7].

At least three approaches are being explored to augment the vaccine responsiveness of immunocompromised populations to enhance their responses to vaccination: (i) revaccination with the same vaccine (i.e., a third dose on an mRNA vaccine (ClinicalTrials.gov Identifier: NCT04885907), (ii) reduced immunosuppression followed by revaccination (ClinicalTrials.gov Identifier: NCT04805125), or (iii) revaccination with a different vaccine.

In solid organ transplant recipients, there is one small, non-randomized publication of revaccination showing that patients with low, detectable levels developed high levels after a booster[8]. The authors state that 44% of patients who were anti-S protein seronegative after the conventional two-dose regimen became seropositive after a third “booster dose” (see adjacent plot). However, a closer look at the data shows that the levels of anti-S antibody after revaccination were much lower in the previously-negative group compared to the previously low-positive group (signal to cutoff ratio 690 ± 293 vs 2676 ± 350). While direct comparisons of these results using U/ml are not possible, we can conservatively assume that the rate of patients achieving the endpoint for our studies (≥ 250 U/ml) would be approximately 20% or less.

The concept of revaccination with a different vaccine (aka heterologous prime boost vaccination) is not a new concept. A landmark study in Macaques demonstrated that a heterologous prime boost approach resulted in superior immunogenicity and enhanced protection from infectious challenge compared to a single vaccine alone [9]-[10]. That study evaluated responses to Simian immunodeficiency virus (SIV) and has been recapitulated in other vaccine models, such as Hepatitis C [11]. Small safety focused studies of a heterologous prime boost strategy in the setting of SARS-CoV2 vaccination have been reported and demonstrate both feasibility and safety of the approach[12] [13]. One study suggested that heterologous prime-boost regimen with an adenovirus vector vaccine also improved Th1-based T cell responses [12], consistent with prior reports that adenoviral vector vaccines drive potent CD8 and CD4 T cell immunity[14].

Based on these data, we have developed the current protocol.

1.2 Investigational Agent

Janssen Ad26.CoV2.S vaccine is comprised of the following ingredients: recombinant, replication-incompetent adenovirus type 26 expressing the SARS-CoV-2 spike protein, Sodium chloride, Citric acid monohydrate, Polysorbate 80, 2-hydroxypropyl- β -cyclodextrin (HBCD), Ethanol (absolute), Sodium hydroxide and Water for injection (WFI).

The Janssen Ad26.COVID-19 vaccine will be supplied at a concentration of 1×10^{11} vp/mL in single-use vials, with an extractable volume of 0.5 mL, and dose at 5×10^{10} vp. It is a single dose vaccine of 0.5mL administered via intramuscular injection, typically in the deltoid muscle.

1.3 Clinical Data to Date

Kidney Transplant Patients at Mayo Clinic: The Study Cohort

The 3 Mayo Clinic transplant sites (located in Rochester, MN, Phoenix, AZ and Jacksonville, FL) collectively perform more than 900 kidney transplants per year and follow more than 5000. Many clinical trials are performed simultaneously across all 3 sites. Over the past 7 years, total enrollment in clinical trials across all sites has been more than 1500 patients. Two of these studies involved more than 500 patients in each trial, demonstrating Mayo Clinic's ability to implement large clinical trials.

Vaccinated Patients

The number of solid organ transplant recipients seen at Mayo Clinic with EPIC documented vaccination (multiple dates of Moderna/Pfizer; or 1 Janssen) as of July 2021 is shown in the table below.

Mayo site	Heart	Kidney	Liver	Lung	Pancreas	Total
Jacksonville	108	583	613	159	11	1474
Phoenix	109	461	319		7	896
Rochester	170	2014	903	56	68	3211
Total	387	3058	1835	215	86	5581

A similar percentage of transplant recipients were vaccinated with the Pfizer (49%) and Moderna (47%) vaccines. Only 4% have received the Janssen Ad26.CoV2.S vaccine.

VACCINE_DESCRIPTION	# Pts	%
SARS-COV-2 (COVID-19) - JANSSEN (J&J)	242	4%
SARS-COV-2 (COVID-19) - MODERNA	2596	47%
SARS-COV-2 (COVID-19) - PFIZER	2749	49%

Anti-SARS-CoV-2 Spike Protein Antibody Testing and Rationale for the Primary Endpoint

Mayo Clinic has reviewed and tested multiple platforms for anti-SARS-CoV-2 spike protein antibody determination. The one selected for use is the Roche Elecsys® Anti-SARS-CoV-2 S, assay which is a one-step double antigen sandwich assay, which has a linear range of antibody determination from 0.4 to 250 U/ml. It is currently unknown what level of antibody response is associated with maximal protection from SARS-CoV2 infection or COVID disease. Our rationale for adopting a level of ≥ 250 U/ml is presented here.

Rationale for Anti-SARS-CoV-2 Spike Protein Antibody Levels as Endpoints

Early after receiving an mRNA COVID vaccination, most of the general population achieves an anti-SARS-CoV-2 spike protein antibody ≥ 250 U/ml (Figure on the right from Naaber et al. [5]). Anti-SARS-CoV-2 spike protein antibody levels do decrease with time, but almost all patients in this study from Europe continued to have levels ≥ 250 U/ml. Given that vaccination in the general population results in protection from severe disease in the vast majority of patients, there is a high correlation between high anti-SARS-CoV-2 spike protein antibody levels and protection from severe disease.

[figure not shown]

Fig. 1. Antibody responses in individuals vaccinated with Pfizer-BioNTech Comirnaty vaccine. S-RBD IgG levels before vaccination (B1D, n=88), after the single (B2D, n=111) and two-dose immunizations (1 week (1wA2D, n=106); 6 weeks (6wA2D, n=89), 12 weeks (12wA2D, n=90), and 6 months (6mA2D; n=84) in vaccinated individuals compared with post-infection levels in patients recovered from COVID-19 (COVID-19, n=97) and pre-COVID-19 negative controls (NC, n=50). The box plot comparisons were performed with the Kruskall-Wallis test and Dunn's multiple testing correction; p-values >0.0001 are reported as exact numbers.

In contrast, several studies mentioned above have shown that **a large percentage of transplant patients form no anti-SARS-CoV-2 spike protein antibody or have levels <250U/ml even early after vaccination.** While a direct correlation between any specific anti- SARS-CoV-2 spike protein antibody has not been studied extensively, transplant patients do appear to have higher rates of COVID infections and possibly higher mortality rates.

No specific anti-spike protein antibody level is supported by the literature, but a level of <250 U/ml is clearly below the levels achieved both early and at 6 months after vaccination in the general population. Thus, we have chosen 250 U/ml (the saturation level of the assay below which does not require dilutions) as the target level of anti- SARS-CoV-2 spike protein antibody because we consider that a “normal” response to vaccine. There is no data for intermediate levels of antibody (likely the higher the better the protection). So, in the absence of any intermediate level data, we are aiming to achieve a normal response in transplant recipients receiving the Janssen Ad26.COV2.S vaccine in our trial.

Mayo Clinic Experience with Anti-SARS-CoV-2 Spike Protein Antibody Testing in Transplant Recipients

As of August 2021, more than 400 anti-SARS-CoV2 spike protein antibody tests had been performed in the Mayo Clinic solid organ transplant recipient population. Of these, 245 were in patients with documented vaccination post-transplantation. The time from vaccination to anti-SARS-CoV-2 spike protein test averaged 72 days (Range 1-181d) The majority of recipients had no response (51%) or had a low-level response (<250 U/ml, 33%). Only 16% had a value ≥ 250 U/mL of anti-SARS-CoV-2 spike protein antibody.

Post-Vaccination Spike protein result			
No_Responder	<250 U/ml	>250 U/ml	Total
125	81	39	245
51%	33%	16%	100%

In stark contrast to the response rate to the COVID-19 vaccine series post-transplant, if a recipient received vaccination prior to transplant, then 61% (1423) of patients had a response ≥ 250 U/ml. Nine patients had a low response (<250 U/mL) with 3 between 50-250 U//ml and 6 <50 U/ml). These data are similar to the overall Mayo Clinic patient cohort tested to date. Among >3800 anti-SARS-CoV-2 spike protein antibodies test results 56% of patients have a value ≥ 250 U/ml by 28 days post-vaccination.

COVID Infections and Deaths

Recent studies have suggested that solid organ transplant recipients have 4 times the rate of death after COVID infection compared to the general population (reviewed by Osmanodja et al[15]) suggesting that transplant recipients have mortality rate with COVID infection 4 times that of otherwise healthy people. At Mayo, the overall known mortality rate has been 3.8% compared to a

mortality rate of 0.8% in the general population—almost exactly the 4 time observed in other studies.

As of August 1, 2021, using the Mayo clinic COVID data registry, we identified 25 patients with breakthrough infection despite re-vaccination. Nine patients required oxygen therapy, 1 required mechanical ventilation support and 1 ECMO. None of the fully vaccinated individuals have died. [16]

1.4 Dose Rationale

The dose of Janssen Ad26.COV2.S vaccine used in this study will be the dose with EUA by the FDA[17]. Data on that dose are summarized here.

The dose level of Janssen Ad26.COV2.S vaccine to be assessed in the present study (5×10^{10} vp) is based on other Ad26-vectored vaccines administered to adults in clinical studies including Ad26.ZEBOV (Ebola virus program); Ad26.ENVA.01, Ad26.Mos.HIV, and Ad26.Mos4.HIV (HIV program); Ad26.CS.01 (malaria program); Ad26.RSV.FA2 and Ad26.RSV.preF (RSV program); and Ad26.ZIKV.001 (Zika virus program). Studies with Ad26.RSV.preF also included participants aged ≥ 60 years. The dose level of 5×10^{10} vp is the most extensively tested dose to date and has shown to be well tolerated and immunogenic in these vaccine programs.

Initial immunogenicity and safety data (28 days post dose 1 from Cohort 1a) from study VAC31518COV1001 has demonstrated that a single dose with the 5×10^{10} vp and 1×10^{11} vp Janssen Ad26.COV2.S vaccine dose levels is immunogenic (according to the study's prespecified criteria) and safe in adults ≥ 18 - ≤ 55 year of age. The sponsor has therefore decided to proceed with the Janssen Ad26.COV2.S vaccine at a dose level of 5×10^{10} vp in the Phase 3 studies.

Non-human primates immunized with a single-dose of Janssen Ad26.COV2.S vaccine (Study 20-14, dose level titration study) showed robust protection after intranasal and intratracheal challenge with SARS CoV-2. Janssen Ad26.COV2.S vaccine at 5×10^{10} vp provided complete protection in the lung in 5 of 5 animals, and in 5 of 6 animals in the upper respiratory tract. All control animals showed substantial viral load in both the lower and upper respiratory tract.

Use of the Janssen Ad26.COV2.S vaccine has not been studied extensively especially after mRNA vaccines. Recently some data was published in the interim results from the NIAID MixNMatch study on a pre-print server [18]. The findings noted homologous and heterologous boosters were overall well-tolerated and immunogenic. Similarly, currently, there are limited published data on optimal timing between 2 doses of the Janssen Ad26.COV2.S vaccine. Data published in Janssen's VRBPAC briefing document note that the number of participants in clinical trials that have received a second dose between 2 to greater than 6 months is 9,379 for those 18 and older and 2,383 for those 60 and older [19]. From these clinical trials, no new safety concern have been identified after a second dose. The reactogenicity after dose two was noted to be similar or milder than the first dose. In the current protocol, all patients will be at least 3 months from their last mRNA vaccine and at least 29 days from their last Janssen Ad26.COV2.S vaccine.

1.5 Risks and Benefits

More detailed information about the known and expected benefits and risks of the Janssen Ad26.CoV2.S vaccine may be found in the IB and its addenda (if applicable) [25].

1.5.1 Risks Related to Study Participation

The following potential risks of the Janssen Ad26.CoV2.S vaccine will be monitored during the study and are specified in the protocol.

1.5.2 Risks Related to Janssen Ad26.CoV2.S Vaccine

Recent data generated from the ongoing clinical studies VAC31518COV1001, VAC31518COV1002, VAC31518COV2001 and VAC31518COV3001, demonstrated that a single dose of the Janssen Ad26.CoV2.S vaccine has an acceptable safety and reactogenicity profile and is sufficient to elicit SARS-CoV-2 neutralizing antibodies in adults ≥ 18 years of age, including adults ≥ 60 years of age when compared to no vaccine.

For emerging clinical data and the most comprehensive nonclinical information regarding the Janssen Ad26.CoV2.S vaccine, refer to the latest version of the IB and its addenda (if applicable) [20-25].

Sites will advise participants that side effects include fever as well as injection site pain, headache, fatigue, myalgia, and nausea per the current ICF; however, the occurrence of fever appears to be more common in younger adults and can be severe. This is based on information from study VAC31518COV1001.

Anaphylaxis is considered an important identified risk for the Janssen Ad26.CoV2.S vaccine. Individuals should be observed by a healthcare provider after vaccination per protocol requirements. Refer to the latest version of the IB and its addenda (if applicable) for further details [20-25].

1.5.2.1 Thrombosis with Thrombocytopenia Syndrome [TTS]

Thrombosis in combination with thrombocytopenia (thrombosis with thrombocytopenia syndrome [TTS]), in some cases accompanied by bleeding, has been observed very rarely following vaccination with the Janssen Ad26.COV2.S vaccine. Reports include severe cases of venous thrombosis at unusual sites such as cerebral venous sinus thrombosis (CVST), splanchnic vein thrombosis, and arterial thrombosis, in combination with thrombocytopenia. Cases of TTS occurred mostly within the first 3 weeks following vaccination, in males and females 18 years of age and older and were reported more frequently in females under 50 years of age. Fatal outcomes have been reported. The exact physiology of TTS is unclear. Thrombosis with thrombocytopenia, following administration of Ad26.COV2.S has a clinical course that resembles autoimmune heparin-induced thrombocytopenia (HIT) (Areppally

2021). Individuals who have experienced TTS or HIT are not eligible for participation in clinical studies.

Individuals diagnosed with thrombocytopenia within 3 weeks after vaccination should be actively investigated for signs of thrombosis. Similarly, individuals who present with thrombosis within 3 weeks of vaccination should be evaluated for thrombocytopenia.

TTS is considered an important identified risk for the Janssen Ad26.COVID-19 vaccine. Participants should be instructed to seek immediate medical attention if they develop symptoms such as shortness of breath, chest pain, leg swelling, persistent abdominal pain, severe or persistent headaches, blurred vision, and skin bruising and/or petechiae beyond the site of vaccination. The medical management of thrombosis with thrombocytopenia is different from the management of isolated thromboembolic diseases. Study site personnel and/or treating physicians should follow available guidelines for treatment of thrombotic thrombocytopenia (e.g., from the American Society of Hematology [26], British Society of Haematology – Expert Haematology Panel [27], and the CDC [28]). The use of heparin may be harmful and alternative treatments may be needed. Consultation with a hematologist is strongly recommended. Management of the participant should not be delayed. Refer to the latest version of the IB and its addenda (if applicable) for further details. Due to the possibility of the occurrence of TTS after vaccination with the Janssen Ad26.COVID-19 vaccine, additional reporting and data collection procedures have been included in the study for thrombotic events, thrombocytopenia, and TTS (see Section 7.2.3), which may facilitate diagnosis and clinical management of the event.

Similarly, TTS is considered to be an adverse event of special interest (AESI). Due to their immunosuppression and underlying diseases, kidney transplant recipients have fluctuations in their platelet counts below the typical reference range among the general population ($>150,000/\mu\text{l}$). A platelet count $>75,000/\mu\text{l}$ is required for inclusion in this trial. The following will be considered as suspected AESIs and will be reported to the sponsor-investigator, Janssen, IRB and DSMB within 1 business day of awareness:

- Platelet count below $150,000/\mu\text{l}$ after receiving the Janssen Ad26.COVID-19 Vaccine without any identifiable alternative cause as determined by the study physicians,
- Platelet count below $150,000/\mu\text{l}$ and a decrease $\geq 25\%$ from baseline after receiving the Janssen Ad26.COVID-19 Vaccine, or
- Any thrombotic event without any identifiable alternative cause as determined by the study physicians will be considered as suspected AESIs and will be reported to the sponsor-investigator, Janssen, IRB and DSMB within 1 business day of awareness.

See Section 7.2.3 for the management of patients with suspected TTS.

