 - All vaccine recipients will remain under observation at the study site for at least 30 minutes after each vaccination to monitor for the development of acute reactions.
 - The sponsor-investigator or the designee will document AEs and SAEs and medically-attended adverse events (MAAEs) for all participants as indicated in Section [7](#).
 - TTS is considered to be an adverse event of special interest (AESI) (Section [7.2.2.1](#)). Suspected AESIs (thrombotic events and thrombocytopenia) must be reported as per Section 7.2.2 and Section [7.3](#) within 1 business day of awareness. Suspected AESIs will be followed up as described in the Schedule of Events in Section 6.6.
 - Any clinically significant abnormalities (including those persisting at the end of the study/early withdrawal) will be followed by the sponsor-investigator until resolution or until clinically stable.
 - A Data Safety Monitoring Board will be established to monitor safety data on an ongoing basis to ensure the continuing safety of the participants enrolled in this study. This committee will review interim unblinded data. The DSMB responsibilities, authorities, and procedures will be documented in its charter. Additional ad hoc review may be performed further to the occurrence of any SAE leading to a study pausing.

Benefit-Risk Assessment for Segment II: A Second Janssen Ad26.CoV2.S vaccine with Immunosuppression Adjustment

Segment II involves a second Janssen Ad26.CoV2.S vaccine with immunosuppression adjustment. The subset of patients in Segment I who did not have immunosuppression adjustment will be offered a second Janssen Ad26.CoV2.S vaccine with adjustment of their immunosuppression. The risks of receiving a second Janssen Ad26.CoV2.S vaccine in immunocompromised populations are unknown. Clinical trials presented from the VRBPAC briefing document showed no new safety concerns identified after a second dose and that reactogenicity of a second dose was similar or milder than after the first dose [19]. SAEs and AEs will be monitored as in Segment I. The risk of immunosuppression adjustment will likely be the same as in Segment I and these will be monitored similarly.

2 Study Objectives

Primary Objectives

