7.2.2 Adverse Events of Special Interest

Adverse events of special interest (AESIs) are significant AEs that are judged to be of special interest because of clinical importance, known or suspected class effects, or based on nonclinical signals. Adverse events of special interest will be carefully monitored during the study by the sponsor-investigator.

AESIs must be reported to Janssen within 1 business day of becoming aware of the event, irrespective of seriousness (i.e., serious and non-serious AEs) or causality following the procedure described above for SAEs. Suspected AESIs will be reported from the moment of vaccination until the completion of the participant's last study related procedure.

Specific requirements for the AESI are described below.

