7.2.2.1 Thrombosis with Thrombocytopenia Syndrome

As described in Section 1.5.2, Risks Related to Study Janssen Ad26.CoV2.S vaccine, TTS has been observed very rarely following vaccination with the Janssen Ad26.CoV2.S vaccine and is considered to be an AESI in this study.

TTS is a syndrome characterized by a combination of both a thrombotic event and thrombocytopenia. TTS is rare and not completely understood. Because of this, all cases of thrombosis and/or thrombocytopenia meeting the criteria below will be considered a suspected case of TTS until further adjudication can be performed. A Janssen AESI Adjudication Committee with appropriate expertise has been established to evaluate suspected AESI and determine whether it is a case of TTS. The sponsor-investigator shall be responsible for reporting any suspected AESI of TTS using the SAE form and the form detailed in Section 14.1.

Due to their immunosuppression and underlying diseases, kidney transplant recipients have fluctuations in their platelet counts below the typical reference range among the general population ($>150,000/\mu\text{l}$). A platelet count $>75,000/\mu\text{l}$ is required for inclusion in this trial. The following will be considered as suspected AESIs and will be reported to the sponsor-investigator, Janssen, IRB and DSMB within 1 business day of awareness:

- Platelet count below $150,000/\mu\text{l}$ after receiving the Janssen Ad26.CoV2.S Vaccine without any identifiable alternative cause as determined by the study physicians,
- Platelet count below $150,000/\mu\text{l}$ and a decrease $\geq 25\%$ from Baseline after receiving the Janssen Ad26.CoV2.S Vaccine, or
- Any thrombotic event without any identifiable alternative cause as determined by the study physicians.

Symptoms, signs, or conditions suggestive of a thrombotic event should be recorded and reported as a suspected AESI even if the final or definitive diagnosis has not yet been determined, and alternative diagnoses have not yet been eliminated or shown to be less likely at the time of the event. Follow-up information and final diagnoses, if applicable, should be submitted to the sponsor-investigator and Janssen as soon as they become available.

In the event of thrombocytopenia, study site personnel should report the absolute value for the platelet count and the reference range for the laboratory test used.

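### The suspected-TTS reporting criteria have no entry for a clot together with a low platelet count, so a narrow class of combined cases can miss TTS reporting and adjudication

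*Combined protocol and SAP*

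**What the plan says.** Section 7.2.2.1 describes TTS as a thrombotic event and thrombocytopenia occurring together, and gives the decision on what is TTS to an adjudication committee. Its gateway sentence reads: "all cases of thrombosis and/or thrombocytopenia meeting the criteria below will be considered a suspected case of TTS until further adjudication can be performed". The criteria, which also stand in Section 1.5.2.1, are joined by *or*:

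1. A post-vaccine platelet count below 150,000/µL, but only "without any identifiable alternative cause as determined by the study physicians".
2. A post-vaccine count below 150,000/µL with a fall of at least 25% from baseline. No condition on cause is attached.
3. A clot, with the same condition on cause as the first: "Any thrombotic event without any identifiable alternative cause as determined by the study physicians will be considered as suspected AESIs".

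Other places describe the same events without a condition on cause:

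- Section 7.2.2 requires AESIs to be reported within one business day, "irrespective of seriousness (i.e., serious and non-serious AEs) or causality".
- The Benefit-Risk Assessment of Study Participation (within Section 1.5.10) says: "Suspected AESIs (thrombotic events and thrombocytopenia) must be reported as per Section 7.2.2".
- Section 7.2.2.1 asks for anti-PF4 testing after either a clot or thrombocytopenia.

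Section 7.2.2.1 also requires anything suggestive of a clot to be reported as a suspected AESI "even if the final or definitive diagnosis has not yet been determined, and alternative diagnoses have not yet been eliminated".

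Section 1.5.2.1 refers the reader to Section 7.2.3 twice, once for TTS reporting and data collection and once as follows: "See Section 7.2.3 for the management of patients with suspected TTS". Section 7.2.3 is headed Pregnancy.

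**The concern.** The syndrome is defined by two findings together, but each criterion looks at one finding alone, and two of the three drop out when another cause is named. A patient can have both findings and still not pass the gateway to adjudication. The question of cause, which the adjudicators are there to weigh, is then settled before they see the case.

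TTS is an important identified risk of this vaccine (Section 1.5.2.1), and the occurrence of AESIs is a listed safety endpoint (Section 3.6). An incomplete entry rule can make the TTS count too low. There is also an indirect link to Segment II: footnote a of Schedule of Events 3 makes entry depend on the absence of SAEs or AESIs associated with the first Janssen dose, so whether an event was classed as an AESI can matter there.

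**Working it through.** The plan states no figure to reproduce. The check applies the three criteria as a logical rule and then finds when a combined case passes through.

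**Inputs**

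- Platelet threshold of 150,000/µL and relative fall of 25%: Sections 1.5.2.1 and 7.2.2.1.
- Platelet count above 75,000/µL on the day of vaccination: Section 4.1.
- Assumption: baseline means the count on the day of vaccination.

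**Step 1: the logic.** Let B be the baseline count and P the post-vaccine count. A patient with a clot and P < 150,000 meets no criterion only if all three of these hold:

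- the clot has another identified cause (otherwise criterion 3 applies);
- the low count has another identified cause (otherwise criterion 1 applies);
- (B − P)/B < 0.25 (otherwise criterion 2 applies).

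**Step 2: the range.** The third condition is P > 0.75 × B. Together with P < 150,000 the window is

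0.75 × B < P < 150,000,

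which is non-empty only if B < 150,000/0.75 = 200,000/µL.

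| Baseline (/µL) | Post-vaccine counts whose reporting depends on cause (/µL) |
|---|---|
| 76,000 | above 57,000, below 150,000 |
| 100,000 | above 75,000, below 150,000 |
| 140,000 | above 105,000, below 150,000 |
| 150,000 | above 112,500, below 150,000 |
| 180,000 | above 135,000, below 150,000 |
| 190,000 | above 142,500, below 150,000 |
| 200,000 or more | none |

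**Step 3: examples, each with a clot and with both findings attributed to another cause.**

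- 180,000 to 140,000: fall 40,000/180,000 = 22.2%. No criterion is met.
- 140,000 to 106,000: fall 34,000/140,000 = 24.3%. No criterion is met.
- 180,000 to 130,000: fall 50,000/180,000 = 27.8%. Criterion 2 is met whatever the causes.

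**Step 4: what a case in the window loses.** Section 7.2.2.1 ties the Section 14.1 form and the adjudication committee to suspected AESIs. A case that meets no criterion need not receive either. If it is serious, Section 7.3 still sends it to Janssen within one business day as an SAE. If it is judged non-serious, the reporting table in Section 7.3 sends it with the monthly transfers, as a medically attended or other non-serious event.

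**Step 5: comparison with the other AESIs.** Section 7.2.2.2 treats all cases of Guillain-Barré syndrome as AESIs pending evaluation, and Section 7.2.2.3 does the same for myocarditis and pericarditis. Neither excludes a case because another cause has been identified. TTS is the only one of these with such a condition.

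**The case against.** Much of the ground is already covered, and four points on the other side stand.

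- **Criterion 2 has no condition on cause.** A reader might infer that any clot with a low count can be removed by naming another cause. That is not so. Any fall of 25% or more to below 150,000/µL brings the patient in, and from a baseline of 200,000/µL upward every count below 150,000/µL does.
- **Suspected clots are reported early.** Section 7.2.2.1 calls for reporting while alternatives are still open, so the condition on cause takes effect only when another cause has already been identified.
- **Section 7.2.2 is not flatly contradicted.** Its rule on causality governs events already classed as AESIs, whereas the condition on cause sits in the definition of a suspected AESI. The Benefit-Risk text is a summary that itself defers to Section 7.2.2. This is a tension between definition and reporting rule.
- **The events do not disappear.** Serious ones reach Janssen on the same form and deadline as AESIs, anti-PF4 testing is asked for, and Section 1.5.2.1 says that either finding within three weeks of vaccination should prompt evaluation for the other. What can be lost is the suspected-TTS label, the Section 14.1 form and adjudication.

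It is also fair to say that for baselines already below 150,000/µL the window includes counts that have not changed or have risen, for example 100,000 to 140,000. Section 1.5.2.1 notes that counts in this population fluctuate below the usual range, which is a reason for some condition on an isolated low count.

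None of this closes the gap for the combination: once another cause has been identified for each finding, the early-reporting sentence no longer decides the matter and no criterion applies.

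**Conclusion.** The gap is real and narrow. It needs a clot, a post-vaccine count below 150,000/µL, a fall of less than 25% (hence a baseline below 200,000/µL), and another cause identified by the study physicians for both findings. Such a case need not be reported as suspected TTS or adjudicated.

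The number of patients affected cannot be estimated. The documents give neither a baseline platelet distribution nor a frequency for the joint condition. The window is not empty, because entry is allowed from just above 75,000/µL and counts are said to fluctuate below 150,000/µL. The number is nevertheless likely to be small: about 400 patients are vaccinated, and Section 1.5.2.1 describes TTS as very rare.

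A reader might go further and infer that the TTS count will be biased between sites or randomized arms, or that another cause can nearly always be found in these patients. The documents support neither. The criteria are worded identically for everyone vaccinated, the judgement is given to the study physicians without further detail, and fluctuating counts do not show that an explanation is always at hand.

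The reference to Section 7.2.3 is a separate, plain error.

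**What to change.** In Sections 1.5.2.1 and 7.2.2.1, add a fourth reporting criterion: any thrombotic event with a post-vaccine platelet count below 150,000/µL is a suspected AESI whether or not another cause has been identified. Record the alternative cause on the Section 14.1 form so that the adjudicators can weigh it.

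Keep the existing condition on cause for an isolated clot or an isolated low count. Removing it from every clot would go beyond the gap shown here and would be a trade-off for the sponsor to make.

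Reconcile the criteria with Section 7.2.2, with the anti-PF4 sentence in Section 7.2.2.1 and with the Benefit-Risk text, so that all describe the same set of events. Change both references to Section 7.2.3 in Section 1.5.2.1 to Section 7.2.2.1.

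The cost is protocol wording and a few extra AESI forms, some of them for clots in patients whose count was already low and stable. The threshold, form and committee already exist, and no visit, dose or treatment rule changes.
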